8.1 SUBJECT DISPOSITION

The subject disposition summaries will be presented by allocated treatment group and overall on the randomized population.

The number and percentages of subjects in each analysis population will be summarized.

The summary of subject disposition will be showing the number and percentages of subjects belonging to the following categories:

- Subjects treated (i.e. with at least one capsule of received treatment selfadministration);
- Subjects for whom the received treatment is different from the allocated treatment;
- Subjects who completed the treatment period (i.e. attended visit Week 24);
- Subjects who discontinued from the treatment period and the reasons for discontinuation;
- Subjects who completed the follow-up period (i.e. attended the follow-up visit Week 28);
- Subjects who discontinued from the follow-up period and the reasons for discontinuation.

Information on analysis populations, study completion and discontinuation will also be displayed in subject listings.

8.2 PROTOCOL DEVIATIONS AND/OR VIOLATIONS

The full list of types of protocol deviations (PDvs) and their relation to the analysis sets, along with the method of identification of each PDv, are detailed in the protocol deviation criteria form which is separate to this SAP. Major PDvs are identified as 'key' deviations on the protocol deviation criteria form. This will be used as a basis for identifying subjects with PDvs throughout the study.

Protocol deviations noted during the trial by the Clinical Research Associates (CRAs), Medical Monitors or Data managers will be tracked throughout the study. In addition, PDvs will be identified programmatically in SAS[®] using data from the clinical database.

At the PDvs review meetings, a consolidated list of PDvs will be reviewed by the team. Prior to database lock, there will be a final review of PDvs and an agreement on the subjects final membership to or exclusion from each analysis set.

Key PDvs as well as other PDvs-related events will be summarized separately by PDv category and preferred term on the ITT population.

A listing presenting all key PDvs as well as other PDvs-related events by patient will also be provided.

8.3 DEMOGRAPHIC AND BASELINE CHARACTERISTICS

The following demographic and baseline characteristics will be summarised by allocated treatment group and overall, on the ITT population:

- Age
- Age (< 65 years, \geq 65 years)
- Sex
- Race
- Ethnicity
- Height
- Weight
- Body mass index (BMI), derived as: weight (kg)/ height(m)^2
- Child bearing potential status (females only)
- Country
- Stratification factor (disease severity level based on baseline serum GGT: < 2.5 x ULN, ≥ 2.5 x ULN)

Separately, the following disease characteristics will be summarised by allocated treatment group and overall on the ITT population:

- Duration of PBC: Time between diagnosis of BPC and randomization, derived as the number of months between the BPC diagnosis date and the randomization date: (date of randomization – date of BPC diagnosis)/30.4375
- PBC diagnosis age
- Liver biopsy at the BPC diagnosis date (Yes, No)

- Stage of liver fibrosis at the BPC diagnosis date (from 0 to 4)
- History of liver decompensation (Yes, No)
- Bleeding from oesophageal varices (Yes, No, Unknown)
- Upper Gastrointestinal bleed (Yes, No, Unknown)
- Ascites (Yes, No, Unknown)
- Spontaneous bacterial peritonitis (Yes, No, Unknown)
- Encephalopathy (Yes, No, Unknown)
- Baseline UDCA dose
- Duration of UDCA treatment: Time between start of UDCA treatment and randomization, derived as the number of months between the start date of UDCA treatment and the randomization date: (date of randomization start date of UDCA treatment)/30.4375
- Baseline serum GGT
- Baseline serum ALP
- Baseline serum ALT
- Baseline serum AST
- Baseline total serum bilirubin
- Baseline serum hsCRP

In addition, listings of the above variables will be produced.

8.4 MEDICAL HISTORY

Medical history is defined as a medical (or surgical) history reported in e-CRF not ongoing at the date of first dose.

Concomitant disease is defined as a medical (or surgical) history reported in e-CRF ongoing at date of first dose.

Medical histories and concomitant diseases will be coded using MedDRA.

Summaries of subjects' medical histories and concomitant diseases will be displayed by system organ class and MedDRA preferred term for each allocated treatment group and overall on the ITT population.

Listing of medical history will be produced. Also, a separate listing presenting surgical and medical procedures will be provided.

8.5 PRIOR AND CONCOMITANT MEDICATIONS

Medications other than GKT137831 will be coded using the WHO-DRUG dictionary. Medications will be defined as follows:

- Prior Medication: Any medication whose end date is before the date of first dose.
- Concomitant Medication: Any medication that started before the date of first dose and stopped on (or is ongoing after) the date of first dose OR any medication whose start date is either the same as (or after) the date of first dose.

In case of partial start and end dates, the imputation rules detailed in section 6.2 will be used. Any medication with a missing end date will be assumed to be a concomitant medication. Summaries of subjects' prior and concomitant medications will be displayed by INN class and preferred term for each dose group and overall on the Safety population.

In addition, a listing of prior and concomitant medications will be presented with associated flags to identify these two categories of medications.

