#### **Prior and Concomitant Medications:**

The number and percentage of subjects taking a medication will be summarized by treatment group, anatomical therapeutic chemical level 2 and preferred term. Summaries will be produced for any medications started prior to first dose (and ongoing at baseline) and medications started on or after the date of first dose.

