#### Adverse Events of Special Interest:

Potential effect of GKT137831 on arterial blood pressure and its clinical relevance will be evaluated. Systolic and diastolic blood pressure values will be examined together with temporally associated blood pressure related events including adverse events and serious adverse events, changes in study drug administration and other related changes in concomitant medications. Medical history and other possible contributing risk factors will also be assessed. Results will be presented by treatment group and planned visit.

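### SAP 8.5 drops the protocol's separate by-arm summary of medications started on or after first dose and replaces ATC level 2 with an undefined 'INN class', declaring neither change

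*SAP*

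**What the plan says.** Protocol 10.4.3.4, under Prior and Concomitant Medications, has the number and percentage of subjects taking a medication "summarized by treatment group, anatomical therapeutic chemical level 2 and preferred term". It asks for summaries of "any medications started prior to first dose (and ongoing at baseline) and medications started on or after the date of first dose".

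SAP 8.5 draws the line elsewhere. Its first category is "Prior Medication: Any medication whose end date is before the date of first dose". Its second has two limbs joined by OR: "Concomitant Medication: Any medication that started before the date of first dose and stopped on (or is ongoing after) the date of first dose", and "any medication whose start date is either the same as (or after) the date of first dose". The summaries "will be displayed by INN class and preferred term for each dose group" and overall, on the Safety population. The accompanying listing flags the same two categories and no others. SAP Section 10, the place for declaring changes to planned analyses, mentions only the two-stage timing of the final analysis.

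The protocol's paragraph on adverse events of special interest has blood pressure examined alongside related events, "changes in study drug administration and other related changes in concomitant medications", with results shown by treatment group and visit. SAP 8.10.1 repeats the examination but not the presentation by treatment group. The only AESI output it names is a listing by subject.

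**The concern.** A drug started after first dose can be a response to something that happened on treatment. A drug already being taken at first dose cannot. The protocol keeps the two apart by arm; the SAP does not, and it gives no reason.

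The distinction has a specific use in this trial. The earlier phase 2 study found a statistically significant rise in diastolic pressure (Protocol 2.1.5.2), and the protocol makes blood pressure an AESI to be read together with medication changes. If new antihypertensive starts are counted in the same row as long-standing antihypertensive use, a difference between arms in new starts may be blurred. Conversely, a difference in the merged row cannot be attributed: it may reflect new starts or a chance imbalance at baseline.

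The grouping level is a second, smaller matter. ATC level 2 is a known therapeutic grouping. INN class is not defined in the SAP, so the rows of the table cannot be predicted from the plan.

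**Working it through.** The plan states no figure on this point, so there is none to reproduce. The check is a comparison of the texts, followed by an illustration.

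**1. Where each medication goes**

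| Timing of the medication | Protocol 10.4.3.4 | SAP 8.5 |
|---|---|---|
| Ended before first dose | no summary asked for | prior |
| Started before first dose, ongoing at first dose | summary 1 | concomitant |
| Started on or after first dose | summary 2 | concomitant |
| Grouping | ATC level 2, preferred term | INN class (undefined), preferred term |

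The SAP splits at the end date of the medication; the protocol splits at its start date. The SAP's split therefore cannot give back the protocol's second summary.

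**2. Whether another SAP output supplies it.** None does. SAP 8.10.1 calls for medication changes to be looked at for blood pressure but defines no by-arm table. The interim analysis (Section 9) and the top-line tables (Appendix 1) contain no medication summary. A count of new starts would have to be made by hand from start dates in the listing.

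**3. How the counting rule acts.** SAP 6.6 counts a subject once within a category. A subject who uses a drug at baseline and starts another drug in the same row on treatment adds nothing to that row.

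**4. Illustration.** Input from the documents: 34 subjects per arm (Protocol 10.2). Assumed, because the documents give no rates: new antihypertensive starts in 5/34 on 400 mg BID and 1/34 on placebo, and baseline use b of 20%, 30% or 40%, equal in both arms.

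A separate table, as in the protocol, shows 5/34 = 14.7% against 1/34 = 2.9%, a difference of 11.8 points.

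For a merged row with new starts independent of baseline use, the expected percentage is b + (1 − b)p:

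| b | 400 mg BID | Placebo | Difference |
|---|---|---|---|
| 20% | 0.2 + 0.8 × 0.147 = 31.8% | 0.2 + 0.8 × 0.029 = 22.4% | 9.4 points |
| 30% | 0.3 + 0.7 × 0.147 = 40.3% | 0.3 + 0.7 × 0.029 = 32.1% | 8.2 points |
| 40% | 0.4 + 0.6 × 0.147 = 48.8% | 0.4 + 0.6 × 0.029 = 41.8% | 7.1 points |

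The merged difference is (1 − b)(p₁ − p₀). The proportional fall therefore equals b, here 20%, 30% or 40%, whatever new-start rates are assumed.

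If all new starts occur in subjects not using the class at baseline, the merged percentage is b + p and the difference stays at 11.8 points. If all occur in subjects already using it, each is already counted in the class row, both arms show b, and the difference is 0. The result depends on an overlap that the merged table does not reveal.

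**The case against.** The strongest case against is that this is a descriptive table, with no test attached and no part in the top-line outputs, and that the safety questions have direct measures. Blood pressure is taken at every visit and summarised by arm with shift tables and box plots (SAP 8.10.3). TSH is summarised by arm (SAP 8.10.2). Pruritus is measured by VAS and the PBC-40 itch domain, and several itch drugs are prohibited or must be kept at a stable dose (Protocol 6.6.2). Medication starts are an indirect, secondary signal, and the data are coded and listed in any case. All of this stands, and it limits the weight of the point. It does not supply the count that the protocol planned.

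Four stronger readings are tempting and are not supported:

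- *Newly started drugs are no longer counted by arm.* They are, within the concomitant category for each dose group. Only the separate count is lost.
- *Universal UDCA use dilutes everything else.* Rows are by class and preferred term, so UDCA has its own preferred-term row and does not affect an antihypertensive row. It would saturate an overall row for any concomitant medication, but SAP 8.5 specifies no such row.
- *The merge removes half or more of the signal.* That impression comes from dividing the illustrative differences by their standard errors. The rates are assumed and no standard error is planned for this table. In the percentages a reader would see, the fall is 20-40% under independence and nil if only non-users start.
- *INN class means listing by substance, with no therapeutic grouping.* The SAP sets it above preferred term, so it may be loose wording for a drug class. What can be said is that it is undefined and is not the protocol's ATC level 2.

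**Conclusion.** The departure is real and undeclared: SAP 8.5 replaces a stated protocol rule instead of filling a gap. The loss is a separate by-arm count of medications started on treatment, which the blood-pressure AESI review draws on and no other SAP output provides. The effect is confined to rows that mix baseline use with new starts.

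The size cannot be given from the documents. Under the assumed rates, with starts independent of baseline use, an 11.8-point difference shows as 9.4 to 7.1 points; across all degrees of overlap with baseline use it could lie anywhere from 0 to 11.8. These figures assume equal baseline use in the arms and apply to a class-level row. The primary GGT analysis, its alpha and the sample size are untouched. This is a modest point about safety reporting that should be corrected because correction is easy.

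**What to change.** In SAP 8.5, summarise by treatment group on the Safety population: (a) medications started before first dose and ongoing at baseline; (b) medications started on or after first dose; and, as a third category, the SAP's existing group of medications ended before first dose. Use ATC level 2 and preferred term as in the protocol, and add a listing flag for new starts. If the sponsor prefers its own categories or grouping, define INN class and declare and justify both changes in Section 10.

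Two details belong in the same edit. SAP 8.5 points to Section 6.2 for partial dates, but the rules are in Section 6.3. Those rules place a partial start date in the month, or year, of first dose on the day of first dose, so such drugs would fall in category (b); a footnote should say so.

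The cost is a change of SAP wording, one further table and one listing flag, all from data already to be coded in WHO-DRUG. No new data collection is needed.

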8.6 STUDY DRUG EXPOSURE AND/OR COMPLIANCE

The study drug exposure is defined as the number of days between the first dose and the last dose taken + 1 day, and it will be summarized by allocated treatment for subjects in the Safety population.

Each day during the treatment period, subjects will self-administer 4 capsules in the morning and 4 capsules in the evening.

At each dispensing visit, each subject will be given individual packs containing a number of allocated treatment bottles (70 capsules of 100 mg GKT137831 and/or matching placebo per bottle) as detailed below:

- 2 bottles at baseline/Day 1 (Visit 2) and the self-administration will be performed as follows:
 - When allocated to GKT137831 400 mg OD: 4 capsules of GKT137831 100 mg from one bottle in the morning and 4 capsules of placebo from the other bottle in the evening.
 - When allocated to GKT137831 400 mg BID: 4 capsules of GKT137831 100 mg from one bottle in the morning and 4 capsules of GKT137831 100 mg from the other bottle in the evening.
 - When allocated to placebo: 4 capsules of placebo from one bottle in the morning and 4 capsules of placebo from the other bottle in the evening
- 4 bottles at Week 2 (Visit 3): the self-administration will be performed as described above.
- 6 bottles at Week 6 (Visit 4), Week 12 (Visit 5) and Week 18 (Visit 6): the self-administration will be performed as described above.

In order to assess the compliance, the investigator or designee will count the remaining unused (i.e. returned) capsules of the received treatment at each visit.

The compliance will be recorded in the eCRF.

Overall study drug compliance is assessed as:

The overall study drug compliance calculation assumes a subject starts dosing in the morning and finishes on their last day in the evening. Consideration of the timing (morning/evening) of the first and last dosing will be taken into account for the compliance calculation.

In addition, a compliance per visit will be listed using the same calculation.

Overall study drug compliance will be summarized using descriptive statistics by received

treatment group on the Safety population. The number (%) of subjects with compliance < 80 %, between 80% and 120% and > 120% will also be reported.

All data related to the assessment of the compliance will be listed.

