# 6.3 Criteria for Study Treatment Modification or Discontinuation

AEs will be graded according to the CTCAE grading system. If an AE is not listed in the CTCAE, the Investigator will use a similar 4-point scale (Grade 1 = mild, 2 = moderate, 3 = severe and 4 = life threatening), as described in 9.2.1.1.

In case of a Grade 1 or 2 severity AE, the subject will be treated as deemed appropriate by the Investigator, and treatment with the IMP should be continued as scheduled.

In case of a Grade 3 severity AE, administration of the IMP must be interrupted until the severity of the event has resolved to  $\leq$  Grade 2 and then resumed at 100% of the initial dose and schedule. Treatment withheld due to a Grade 3 severity AE will not be made up later. If a Grade 3 severity AE does not resolve to  $\leq$  Grade 2 within 24 hours of IMP interruption, or if a Grade 3 severity AE recurs after resumption of IMP, the subject must be permanently discontinued from treatment (see Section 5.6.4).

In case of any Grade 4 severity AE, administration of the IMP must be permanently discontinued.

Withdrawals will be handled as described in Section 5.6.5.

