# 6.5 Subject Compliance

The assigned IMP, dosage, timing and mode of administration may not be changed, except as described in Section 6.3. Any departures from the intended regimen must be recorded in the eCRF.

IMP accountability and subject compliance will be documented throughout the study using studyspecific IMP dispensing and return record forms.

Subjects will be asked to return all used IMP, including empty and partially used containers. IMP will be dispensed at baseline/Day 1 (Visit 2), Week 2 (Visit 3), Week 6 (Visit 4), Week 12 (Visit 5) and Week 18 (Visit 6). At Week 2 (Visit 3), Week 6 (Visit 4), Week 12 (Visit 5), Week 18 (Visit 6) and Week 24 (Visit 7), the unused IMP dispensed to the subject at the previous visit will be returned to the Investigator. The Investigator will determine compliance by capsule count per bottle and batch number. Subjects exhibiting non-compliance as assessed by capsule counts will be counseled on the importance of good compliance to the study dosing regimen. Drug non-compliance is defined as taking less than 80% or more than 120% of IMP during the double-blind treatment period.

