### 10.4 Analysis Methods

#### **10.4.1 Analysis Populations**

The **Intent-To-Treat (ITT)** population will include all randomized subjects who receive at least one dose of IMP or placebo. The ITT population will be analyzed by the randomized treatment and will be used as the primary population for all analyses of efficacy.

The **Safety** population will be used for the analysis of all safety data and will include all subjects who received at least one dose of IMP or placebo, irrespective of whether they were randomized. The Safety population will be analyzed by the treatment received.

The **Per Protocol (PP)** population will be a subset of the ITT population and will include all subjects without a major protocol deviation. Protocol deviations will be defined with the classification of subjects excluded from analysis populations prior to unblinding at end of study.

The PP population will be analyzed by the randomized treatment. This population will be for supportive analysis of the primary endpoint and secondary endpoints where deemed relevant.

Major protocol deviations will be summarized by treatment group. All protocol deviations deemed important even if not leading to subject exclusion from the PP population will be listed.

Protocol No.: GSN000300	Compound No.: GKT137831
Protocol Version No.: Final 4.0; Amendment 3	Sponsor: Genkyotex
Protocol Date: 24 July 2018	Author: Cmed Clinical Services

The **Pharmacokinetic (PK)** population will be used for the analysis of pharmacokinetic data and will include all subjects who received at least one dose of IMP, who have at least one valid PK measurement and who have no major protocol deviations relating to PK data. The PK population will be analyzed by the treatment received.

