The Intent-To-Treat (ITT) population will include all subjects randomly allocated to a treatment arm who have received at least one dose of GKT831 or placebo.

The ITT population will be analyzed by the allocated treatment group and will be the primary population for all analyses of efficacy data.

Per Protocol (PP) population

The Per Protocol (PP) population will include the subjects of the ITT population without a major protocol deviation.

The PP population will be regarded as a secondary population for supportive analyses of efficacy data.

The outputs planned for the PP population will be produced only if there are at least 10% fewer subjects in the PP population compared to the ITT population. That being the case, the PP population will be analyzed by the dispensed study treatment.

Protocol deviations will be defined with the classification of subjects excluded from analysis populations at the end of the study prior to unblinding.

Major protocol deviations will be summarized by the allocated treatment group.

All protocol deviations deemed important will be listed even if not leading to subjects' exclusion from the PP population.

Safety population

The Safety population will include all subjects who have received at least one dose of GKT831 or placebo, irrespective of whether they were randomly allocated to a treatment arm, and had at least one safety assessment.

The Safety population will be analyzed by the dispensed study treatment and will be the primary population for all analyses of safety data.

Pharmacokinetic (PK) population

The Pharmacokinetic (PK) population will include all subjects who have received at least one dose of GKT831, have had at least one valid PK measurement and have had no major protocol deviations relating to PK data.

The PK population will be analyzed by the received treatment group and will be the primary population for the analyses of PK data.

8 Methods of Analyses and Presentations

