8.10.1 Adverse Events (AEs)

All AEs will be coded using MedDRA dictionary. The version of the dictionary will be provided in the adverse events tables, figures and listing footnotes.

All information on AEs will be listed by subject.

Treatment-Emergent Adverse Events (TEAEs) will be defined as AEs that started on or after the date of the first dose of the received treatment.

AEs that occurred prior to the first dose of the received treatment and increased in severity and/or relationship after the first dose of the received treatment will also be regarded as TEAEs. If it is not possible to determine whether an AE is a TEAE due to a missing start date, the AE will be regarded as a TEAE unless the stop date indicates that the AE occurred prior to the first dose of the received treatment.

All reported TEAEs will be summarized.

The number and percentage of subjects experiencing the following categories of AEs will be summarized for each received treatment group and for all received treatment groups combined both overall and by system organ class and preferred term:

- TEAEs
- Related TEAEs
- Serious TEAEs
- Related and serious TEAEs
- TEAEs leading to study drug discontinuation
- TEAEs leading to study drug interruption
- Non-TEAEs

In addition, the number and percentage of subjects experiencing the following categories of AEs will be summarized for each received treatment group and for all received treatment groups combined by system organ class, preferred term and maximal severity:

- TEAEs
- Related TEAEs

For all system organ classes and preferred terms with a TEAE incidence rate of at least 5% over all received treatment groups combined, the number and percentage of subjects will be summarized for each received treatment group and for all received treatment groups combined by system organ class and preferred term.

Subjects will be counted only once within each system organ class, preferred term and severity.

- If a subject has experienced more than one adverse events coded within the same system organ class then this subject will be counted only once within that system organ class.
- If a subject has experienced more than one adverse events coded to the same preferred term within a system organ class then the subject will be counted only once for that preferred term and within that system organ class.

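### SAP 8.6 groups study drug exposure by allocated arm, while the Safety population and its companion tables are grouped by the treatment dispensed or received

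*SAP*

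**What the plan says.** SAP 8.6 reports study drug exposure on the Safety population and gives both its definition and its grouping in these words: "the number of days between the first dose and the last dose taken + 1 day, and it will be summarized by allocated treatment". Later in the same section, on the same population: "Overall study drug compliance will be summarized using descriptive statistics by received" treatment group.

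SAP Section 7 sets the grouping for this population: "The Safety population will be analyzed by the dispensed study treatment and will be the primary population for all analyses of safety data". Protocol 10.4.1 puts it as "The Safety population will be analyzed by the treatment received". In SAP 8.10.1 the subject counts for each AE category, in the overall tables and in those split by coded term, "will be summarized for each received treatment group and for all received treatment groups combined both overall".

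Two further provisions bear on the point. The disposition summary in SAP 8.1 counts subjects whose received treatment differs from the allocated one. The Safety population, in both documents, admits treated subjects whether or not they were randomized.

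On interruptions, Protocol 6.3 says that for a Grade 3 AE "administration of the IMP must be interrupted until the severity of the event has resolved" to Grade 2 or lower. Protocol 6.3.1 to 6.3.3 also require interruption for liver signals, anemia and raised TSH, with resumption possible in each case.

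**The concern.** An exposure table gives the context for the AE tables, so the two should describe the same people in the same columns. Here they may not. A subject allocated to one arm and treated with another contributes days to the first arm in the exposure table, and events and capsule counts to the second arm everywhere else. A subject treated without randomization has no allocated arm, so the exposure table as specified cannot place that subject.

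The definition raises a second, smaller matter. A count from first to last dose measures treatment duration. It equals days on drug only if dosing was continuous. A subject who stops for a re-test and then resumes is credited with the days in between.

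Such a mismatch is easy to prevent in the plan. Once the tables have been produced, it has to be explained.

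**Working it through.** The documents state no exposure figure, so there is none to reproduce. The check compares the grouping rules and then bounds the size.

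**1. Grouping rules side by side**

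| Place | What it governs | Grouping |
|---|---|---|
| SAP 8.6 | Exposure, Safety population | allocated |
| SAP 8.6 | Compliance, Safety population | received |
| SAP 7 | Safety population in general | dispensed |
| Protocol 10.4.1 | Safety population in general | received |
| SAP 8.10.1 | AE tables | received |
| SAP 6.6 | Presentation of exposure, among others | allocated or actual, with a pointer to Section 7 |

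Only the exposure sentence fixes allocated treatment. SAP 6.6 does not settle the matter: it defers to Section 7, which says dispensed, while the specific sentence in 8.6 says allocated.

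**2. Size of the grouping mismatch**

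Inputs: 34 subjects per arm (SAP 5.4) and 24 weeks of treatment (SAP 5.2).

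- Full course: 24 × 7 = 168 days.
- Subject-days per arm: 34 × 168 = 5,712.
- One subject on the wrong arm: two arms of 34 and 34 by allocation become 33 and 35 by treatment received.
- Subject-days moved: up to 168, and 168/5,712 = 2.9% of an arm.
- Two such subjects, both moving the same way: 32 and 36; 336/5,712 = 5.9%.

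**3. Size of the interruption effect in one subject**

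For a 168-day span with a resumed gap of g days, days on drug = 168 − g, and the overstatement relative to days on drug = g/(168 − g).

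- g = 1 (a Grade 3 pause that may be resumed; Protocol 6.3 requires resolution within 24 hours): 1/167 = 0.6%.
- g = 3 (upper end of the 2 to 3 days to re-test for liver signals or TSH, Protocol 6.3.1 and 6.3.3): 3/165 = 1.8%.
- g = 7 (limit for the anemia re-test, Protocol 6.3.2): 7/161 = 4.3%.
- Protocol 6.3.1 states no maximum time off drug during the liver work-up. Assuming 14 to 28 days: 14/154 = 9.1% to 28/140 = 20.0%.

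**4. Size of the interruption effect in an arm**

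Arm-level share of the recorded span = (share of subjects with a resumed gap) × g/168. The documents give no interruption rate, so 5% to 20% is assumed.

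- Low: 0.05 × 1/168 = 0.03%.
- High, with gaps up to 7 days: 0.20 × 7/168 = 0.83%.
- Extreme, with 28-day gaps in 20% of subjects: 0.20 × 28/168 = 3.3%.

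**The case against.** The best defense of the grouping is that the mismatch is conditional and visible. If nobody receives the wrong arm and nobody is treated unrandomized, allocated and received groupings give identical tables. If someone does receive the wrong arm, the SAP 8.1 disposition table counts that subject. This stands as a limit on the size, but it does not remove the contradiction. The disposition table is run on the randomized population, so it would not show a treated but unrandomized subject, and it does not realign the exposure columns.

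The best defense of the definition is that first dose to last dose plus one day is clear, reproducible and usable. That also stands: the quantity is sound, and only its label is loose.

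A reader might infer more than the documents support:

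- *That exposure is overstated outright.* The count is too long only when an interruption is followed by resumption. After permanent discontinuation the last dose already ends it. Under Protocol 6.3, a Grade 3 AE that has not resolved to Grade 2 or lower within 24 hours leads to permanent discontinuation, so it adds no further days.
- *That an excess of interruptions on active drug would be hidden.* SAP 8.10.1 tabulates TEAEs leading to interruption by received treatment and lists such AEs by subject. Protocol 9.2.1.3 has laboratory abnormalities that lead to withheld treatment recorded as AEs. SAP 8.6 reports compliance from capsule counts.
- *That AE rates are biased by the exposure count.* SAP 6.6 calculates AE percentages on the number of subjects in the population, not on time.
- *That this is the highest dosing so far.* Protocol 2.2 reports multiple dosing up to 900 mg/day in healthy subjects, against 2 × 400 = 800 mg/day here. The trial is the longest dosing in people that the protocol describes and the highest in patients, but not the highest overall.

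**Conclusion.** The grouping point holds. SAP 8.6 assigns exposure in the Safety population to allocated arms, against SAP Section 7, Protocol 10.4.1, the AE tables and the compliance summary in the same section, and no other provision repairs it. The consequence depends on a dispensing error or an unrandomized treated subject. Per subject given the wrong arm for the whole course, it is one subject in each of two arm denominators and at most 2.9% of an arm's planned subject-days. That figure assumes 34 subjects per arm, all treated for 168 days.

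The interruption point is secondary and concerns labelling. In a subject who resumes, the count exceeds days on drug by 0.6% to 4.3% for gaps of 1 to 7 days, and by more only if a long liver work-up is assumed. At arm level the effect is below 1% for gaps of 1 to 7 days in an assumed 5% to 20% of subjects.

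No planned AE percentage or efficacy result changes. The point is minor.

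**What to change.** In SAP 8.6, summarize exposure by the Section 7 Safety grouping instead of by allocated treatment. Choose one term among dispensed, received and actual, and use it in SAP 6.6, 7, 8.6 and 8.10. Grouping by treatment taken also gives any unrandomized treated subject a column.

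Optionally, rename the first-to-last-dose measure treatment duration. If the eCRF holds interruption start and stop dates, add a row for days on drug, equal to duration minus documented days off. Confirm this first: Protocol 6.5 says "Any departures from the intended regimen must be recorded in the eCRF", which does not establish that dates are captured, and Protocol 6.4 plans no subject diary.

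The main change costs a word in SAP 8.6 and a consistency edit elsewhere. The optional part costs a label and, if the dates exist, one derived variable and one table row. Neither changes the design, the conduct of the trial or the efficacy analyses.
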